F-18 florbetapir has been studied in multiple clinical trials to image beta-amyloid deposition in the brain of subjects with Alzheimers' disease. Florbetapir F-18 has been well tolerated in studies of more than 2000 human subjects. Biodistribution studies in humans revealed predominantly hepatobiliary excretion. The tracer clears rapidly from the blood pool in about 20 minutes (6). This radiotracer has been recently approved for clinical imaging of brain amyloid in subjects with suspected Alzheimer's

disease. In this pilot study, F-18 florbetapir images will be acquired immediately after injection and at 90 minutes after injection to study radiotracer bio-distribution and understand the optimal time for imaging.

Preliminary studies using C-11 labeled PiB (another agent used to image beta-amyloid in the brain of patients with Alzheimer's disease)¹¹ show that this tracer can be taken up by cardiac amyloidosis (unpublished data in abstract form from Uppsala University, Sweden). However, this tracer is produced by a cyclotron and has a short half-life of 20 minutes; hence it can only be used in sites with a cyclotron on site, limiting its applicability for multicenter studies. We propose to test a longer half life tracer, F-18 florbetapir in a pilot study to evaluate their potential utility to image cardiac amyloidosis. If this agents works, that will enable us to plan a large multicenter study of this rare disorder allowing us the potential to detect preclinical disease as well as follow response to therapy.

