Amyloid related heart disease is associated with LV wall thickening due to infiltration; however, this myocardial wall thickening is not definitively distinguishable from left ventricular myocyte hypertrophy from increased afterload to the heart from hypertension or aortic stenosis. Typically myocardial or other tissue biopsy with typical echo features of amyloidosis is required for confirmation of amyloidosis. This pilot study is designed to understand whether we can measure cardiac amyloid burden using a specific radiotracer targeted against amyloid protein (F-18 florbetapir). The longer half-life (120 minutes) of F-18 florbetapir, makes it a more attractive tracer for conducting a multicenter clinical study, since this radiotracer can be delivered to sites without an onsite cyclotron. At this point it is unknown if F-18 florbetapir will bind to either AL or TTR amyloid protein or to both of them or to neither of them. Hence, we would like to study 15patients with AL, 15 patients with TTR amyloidosis and 15 volunteer subjects without amyloidosis [including 10 elderly subjects with clinical heart failure with preserved ejection fraction (HFpEF)] to understand these differences if any. We also seek to understand if the signal to noise ratio of the circulating amyloid protein in the blood pool (AL amyloid disease) allows for good differentiation of myocardial amyloid uptake.

The purpose of the proposed research study is to examine in detail, using quantitative PET, myocardial F-18 florbetapir uptake in cardiac amyloidosis in order to better understand mechanisms of heart damage in this disease. The following specific aim is proposed:

II. SPECIFIC AIM:

The *primary aim* of this pilot study is to determine whether amyloid deposits in the heart can be measured non-invasively by F-18 florbetapir (Trade Name: Amyvid) positron emission tomography (PET) in 10 individuals with documented cardiac amyloidosis and in 5 individuals without cardiac amyloidosis.

A secondary aim of this study is to determine reproducibility of F-18 florbetapir uptake in the myocardium.

III. SUBJECT SELECTION

a) Inclusion and Exclusion Criteria:

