During the course of this research study, we will draw a total of 35-40cc_of blood. This includes 10 cc of blood for oxidative stress markers (if subject provides additional consent), 15 cc of blood for florbetapir metabolite analysis, 10 cc of blood for metabolomics and mito DNA measures (if subject provides additional consent), 5 cc for pregnancy test (in individuals who need them). Pregnant women and breastfeeding women cannot take part in this research study.

Serum F₂-isoprostane and Peroxynitrite— 10 cc of blood samples will be collected in EDTA tube before the PET/CT scan of Study Visit 2 to measure serum markers of oxidative stress. F₂-isoprostanes will be measured in [name] laboratory using serum isolated from whole blood collected with EDTA and stored at -80°C using immunoassay (8-isoprostane EIA kit, Cayman Biochemical). If needed, findings can be confirmed using mass spectroscopy. Nitrotyrosine levels will be measured in serum that is stored at -80°C by immunoassay (Nitrotyrosine EIA kit, Oxis).

Serum metabolomic analysis—10 cc of blood samples will be collected in EDTA tubes before the PET/CT scan of Study Visit 2 for metabolomic and mitochondrial DNA analyses.

Urine Samples: 24 hour urine sample will be collected. The urine samples will be deindentified by a study subject code and used to extract light chains that will be infused into zebra fish with or without pretreatment with rapamycin to study cardiac function and survival.

VI. BIOSTATISTICAL ANALYSIS

This is a pilot feasibility study using F-18 florbetapir. Mean myocardial uptake will be estimated in the subjects. Mean liver to heart ratio will be estimated.

VII. RISKS AND DISCOMFORT

Time: Participation in this trial entails a rest F-18 florbetapir PET/CT scan. The total time spent for the study procedures is approximately 2 hours.

Intravenous line insertion: Possible side effects intravenous line insertion are pain, bruising, or infection where the needle entered the skin. Some people faint or get dizzy during insertion of the intravenous line.

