Study Title: Imaging Cardiac Amyloid Burden: A pilot Study Using F-18 Florbetapir Positron Emission Tomography

NCT Number: NCT01683825

Document Date: January 2018

Analytical Plan

Study Objective(s)

Specific Aim: The *primary aim* of this pilot study is to determine whether amyloid deposits in the heart can be measured non-invasively by F-18 florbetapir (Trade Name: Amyvid) positron emission tomography (PET) in 30 individuals with documented cardiac amyloidosis and in 15 volunteers without cardiac amyloidosis.

A secondary aim of this study is to determine reproducibility of F-18 florbetapir uptake in the myocardium.

Study groups:

Subjects with cardiac amyloidosis and control subjects without cardiac amyloidosis.

Imaging Methods

In this pilot feasibility study, F-18 florbetapir was used to image myocardial amyloid deposits. F-18 florbetapir PET/CT images were acquired in a dynamic mode and reconstructed into static images. Visual assessment and SUV of myocardial uptake of F-18 florbetapir was performed on static images from 4 minutes to 30 minutes. The left ventricular global myocardial F-18 florbetapir images were reviewed in the standard radiological and cardiac imaging planes. We used PMOD software to measure global left ventricular standardized uptake value (SUV) of F-18 florbetapir using SUV mean (SUVmean).

Statistical Methods

This is a pilot feasibility study using F-18 florbetapir to image myocardial amyloid deposits. Mean and maximal myocardial uptake of F-18 florbetapir will be estimated in the subjects with diagnosed cardiac amyloid. Mean liver to heart ratio will be estimated.

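### The SAP gives no reason for its 4-30 min SUV window, and neither document defines a blood-pool measure or a later-window SUV or visual analysis, so the defined SUV measures do not by themselves distinguish myocardial binding from circulating activity.

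*SAP*

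**What the plan says.** **Window.** SAP, Imaging Methods: "Visual assessment and SUV of myocardial uptake of F-18 florbetapir was performed on static images from 4 minutes to 30 minutes". The quantitative measure is a global left ventricular SUVmean. No reason is given for the window, and the protocol does not mention it.

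**Estimates.** SAP, Statistical Methods: "Mean and maximal myocardial uptake of F-18 florbetapir will be estimated in the subjects with diagnosed cardiac amyloid". A mean liver-to-heart ratio is added, without a time window. SAP, Study groups, lists "Subjects with cardiac amyloidosis and control subjects without cardiac amyloidosis", and Protocol VI says more broadly "Mean myocardial uptake will be estimated in the subjects". No comparison between groups is written down.

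**Data collected.** Protocol V (image acquisition) plans 90 minutes of list-mode data from injection, unlisted for analysis into static, gated and dynamic files. Six blood samples over the first 60 minutes are for metabolite analyses.

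**Background.** Protocol I.b contains three statements that bear on the window:
- On clearance: "The tracer clears rapidly from the blood pool in about 20 minutes".
- On timing: images are to be "acquired immediately after injection and at 90 minutes after injection to study radiotracer bio-distribution and understand the optimal time for imaging".
- On AL disease: the investigators want to know whether the signal-to-noise ratio of the "circulating amyloid protein in the blood pool (AL amyloid disease) allows for good differentiation of myocardial amyloid uptake".

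**The concern.** The primary aim is whether cardiac amyloid can be measured with this tracer. The protocol treats binding itself as open: "At this point it is unknown if F-18 florbetapir will bind to either AL or TTR amyloid protein or to both of them", and the sentence goes on to allow for neither. An absolute myocardial SUV taken while tracer is still in the blood contains some circulating activity. Without a blood-pool value beside it, a raised SUV cannot by itself be read as binding.

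Comparison with controls would help in part. It cancels blood signal that is common to both groups, but not blood signal that differs between them. A difference of that kind is what the protocol's AL question raises.

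Two questions in the background section are also left without a defined quantitative analysis: the best imaging time, and differentiation from the blood pool in AL disease. They are distinct. Early tracer clearance bears on the first. The second concerns circulating protein and would still need a blood-pool value in a later window. Both matter for the larger multicenter study that this pilot is meant to inform.

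**Working it through.** The plan states no figure to reproduce on this point, so the check is arithmetic on its own times.

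**Inputs.** Window 4 to 30 min (SAP, Imaging Methods). Acquisition 90 min (Protocol V). Blood-pool clearance c of about 20 min and F-18 half-life of 120 min (both Protocol I.b). Because the clearance time is approximate, I assume a range of 15 to 25 min.

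**1. Share of window time before clearance**, (c - 4)/(30 - 4):
- c = 15: 11/26 = 42%
- c = 20: 16/26 = 62%
- c = 25: 21/26 = 81%

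**2. Share of acquired post-clearance time inside the window**, (30 - c)/(90 - c):
- c = 15: 15/75 = 20%
- c = 20: 10/70 = 14%
- c = 25: 5/65 = 8%

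The 90 - 30 = 60 minutes after the window have no defined SUV or visual analysis.

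**3. What these figures do not give.** They are shares of time. The documents do not say how much tracer is left in blood at 20 min or what shape the clearance curve has. To show how open this is, assume mono-exponential clearance with a fraction r left at 20 min, so k = -ln(r)/20 and mean blood activity from a to b is (e^(-ka) - e^(-kb))/(k(b - a)). The mean over 4-30 min, relative to 20-30 min, is then:
- r = 25%: 0.351/0.180 = 2.0
- r = 1%: 0.0663/0.0039 = 17

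Both r and the curve are assumptions, and the result describes blood, not the myocardial SUV. The blood share of the SUV cannot be computed from the documents, and the conclusion does not use these ratios.

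**4. Are later windows practical?** Decay-only counts relative to 4-30 min are (2^(-a/120) - 2^(-b/120))/(2^(-4/120) - 2^(-30/120)). The denominator is 0.9772 - 0.8409 = 0.1363.
- 20-30 min: 0.0500/0.1363 = 37%
- 30-60 min: 0.1338/0.1363 = 98%
- 60-90 min: 0.1125/0.1363 = 83%
- 30-90 min: 0.2463/0.1363 = 181%

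This assumes that tissue concentration changes only through decay. Washout, unknown here, would lower the figures. They bear on feasibility only and say nothing about bias.

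**5. Could another planned measure serve as the blood reference?** The liver-to-heart ratio does not: Protocol I.b describes excretion as mainly hepatobiliary, so liver activity is not blood activity. The blood samples are assigned to metabolite analyses and linked to no uptake estimate. The 0-3 visual score (Protocol V, interpretation of images) does bear on how well myocardial uptake stands out, but it does not quantify blood activity, and the SAP confines the visual assessment to 4-30 min.

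**The case against.** The strongest reply is that this is a feasibility pilot. Its stated aims are measurability and reproducibility, and the two questions above appear only in the background section. Nothing shows that blood activity in the window is large or that it differs between groups. All of that stands, and it limits the point to an inexpensive improvement.

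Four stronger readings are tempting, and the documents support none of them.

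- **That uptake cannot be separated from circulating tracer in this trial.** This is true of the measures defined, not of the data. List-mode data and dynamic frames would allow a blood-pool region and a later window.
- **That the window is wrong, or that 62% of the SUV is blood.** The 62% is clock time. The clearance remark is a background statement that does not say how complete clearance is.
- **That nothing after 30 minutes is analysed, or that only a blood-pool measure could address the AL question.** The 4-30 minute limit applies to the visual assessment and SUV. The liver-to-heart ratio, the protocol's uptake quantitation and its liver biodistribution carry no time limit, and metabolite sampling runs to 60 minutes. The visual score is also partial evidence on differentiation.
- **That the window was picked after seeing results.** The SAP is dated January 2018 and describes the imaging reads in the past tense, while the protocol's enrollment period runs to October 2018. This makes it reasonable to ask when the window was fixed, but it does not show a data-driven choice.

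**Conclusion.** The point holds in a limited form. The SAP leaves its window unexplained, and 16 of the 26 minutes (42% to 81% over the assumed 15 to 25 min range) precede the protocol's own approximate clearance time. With no blood-pool measure and no later SUV or visual window defined, the planned SUV estimates do not by themselves distinguish binding from circulating activity, and two background questions lack a defined quantitative analysis. The size of the circulating contribution is unknown and may be small. No sample-size or power figure is affected. The change is worth making because it bears on how the primary readout is interpreted, but the gap does not invalidate the 4-30 minute result.

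**What to change.** Keep the 4-30 minute analysis as it is. Add to the SAP a sensitivity analysis, labelled exploratory, from the same list-mode data:

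- Draw a region of interest in the LV cavity as the blood-pool reference.
- Report LV SUVmean, blood-pool SUVmean and the myocardium-to-blood-pool ratio, separately for AL, TTR and control subjects.
- Do this for 4-30 minutes and for at least one window starting after 20 minutes, chosen by the sponsor.
- State why the 4-30 minute window was chosen, and when relative to review of the dynamic data.

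The cost is analyst time for re-binning and one extra region; no new scans are needed. Later windows may hold fewer counts, and the ratio may be noisy when blood activity is low, so blood-pool SUVmean should be shown beside it. A later window would not by itself remove tracer bound to circulating protein, but the blood-pool value would make it visible.

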following one intravenous injection of 10 mCi of F-18 florbetapir. One set of F18 florbetapir images will

be acquired in a 3D list mode starting with the injection of F-18 florbetapir for 90 minutes. Images will

be unlisted and quantitation of radiotracer uptake performed. Mean and maximum F-18 florbetapir

uptake will be measured. Radiotracer biodistribution in the liver and subdiaphragmatic regions will be

measured. A total of 10 AL and 10 ATTR amyloid patients will undergo a repeat F-18 florbetapir PET scan

within a month of the initial study (next day to one month).

5

Number of Subjects Planned

No more than 45 subjects will be enrolled into the study.

Main Selection Criteria

Subjects will be eligible if they meet all of the following inclusion criteria and none of the exclusion criteria:

Inclusion criteria for amyloid subjects:

- Age > 18 years
- Biopsy proven amyloidosis outside the heart with typical echocardiographic appearance of cardiac involvement, or a positive cardiac biopsy.
- Diagnosis of AL amyloidosis by standard criteria (evidence of plasma cell dyscrasia with appropriate tissue staining for AL) OR
- Diagnosis of TTR amyloidosis (no evidence of plasma call dyscrasia and positive TTR staining of amyloid in tissue biopsy)
- Able and willing to provide informed consent to participate in the study
- 10 subjects with HFpEF age >70 years will be included in the control group.

Exclusion criteria for both amyloid and volunteer subjects:

- Pregnancy
- In the 10 subjects with HFpEF age >70 years, prior coronary artery disease, coronary revascularization or severe valvular heart disease
- Serious non-cardiac medical illness (e.g., disseminated malignancy, severe neurological dysfunction at time of baseline PET study) which will preclude research study participation

Statistical Methods:

This is a pilot feasibility study using F-18 florbetapir to image myocardial amyloid deposits. Mean and maximal myocardial uptake of F-18 florbetapir will be estimated in the subjects with diagnosed cardiac amyloid. Mean liver to heart ratio will be estimated.

I. BACKGROUND AND SIGNIFICANCE:

a) Introduction

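### The SAP and Synopsis limit the uptake estimates to amyloid subjects, so the primary aim has no stated control estimate or amyloid-versus-control difference

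*SAP*

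**What the plan says.** **Aim and groups.** The SAP sets the primary aim "in 30 individuals with documented cardiac amyloidosis and in 15 volunteers without cardiac amyloidosis". Under Study groups it lists "Subjects with cardiac amyloidosis and control subjects without cardiac amyloidosis".

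**Reason for the groups.** Protocol section I.b says it is not known whether the tracer "will bind to either AL or TTR amyloid protein or to both of them or to neither of them". It gives this as the reason for enrolling 15 AL, 15 TTR and 15 non-amyloid subjects, "to understand these differences if any". It also asks whether the "signal to noise ratio of the circulating amyloid protein in the blood pool (AL amyloid disease) allows for good differentiation of myocardial amyloid uptake".

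**Measurement.** The design text of the Synopsis sets no group limit: "quantitation of radiotracer uptake performed. Mean and maximum F-18 florbetapir" uptake is to be measured. The 0–3 visual score in Protocol section V has no group limit either.

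**Analysis.** The SAP and the Synopsis share one sentence: "Mean and maximal myocardial uptake of F-18 florbetapir will be estimated in the subjects with diagnosed cardiac amyloid". Protocol section VI says "Mean myocardial uptake will be estimated in the subjects" and does not mention maximal uptake. All three sections add a mean liver-to-heart ratio without naming a group.

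**The concern.** The aim and the list of groups include controls, but the uptake sentence in the SAP and Synopsis leaves them out. Myocardial signal in an amyloid patient combines whatever is bound to amyloid with whatever would be there anyway. A mean in amyloid subjects does not separate the two, so on its own it cannot exclude the possibility, which the background raises, that the tracer binds neither type.

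A comparison can still be made from the planned scans. But the measure, the amyloid grouping (pooled, AL or TTR) and the control set (all 15, or the 10 with HFpEF) are not fixed, and could be chosen once results are known.

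**Working it through.** **1. Compare the three statistical sections.**

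| Section | Mean uptake | Maximal uptake | Liver-to-heart ratio | Control estimate or group difference |
|---|---|---|---|---|
| SAP, Statistical Methods | amyloid only | amyloid only | no group named | none |
| Synopsis, Statistical Methods | amyloid only | amyloid only | no group named | none |
| Protocol VI | the subjects, not specified | absent | no group named | none |

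If Protocol VI means all subjects, it conflicts with the other two. If it means amyloid subjects, controls have no uptake estimate anywhere. In neither case is a difference stated.

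**2. Check the measures.** The SAP Imaging Methods define global left ventricular SUVmean only. The maximal uptake named in the SAP Statistical Methods therefore has no definition in its imaging section.

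**3. What precision would the missing contrast have?** The documents state no SD, expected difference or power target, so there is no plan figure to reproduce. What follows is illustrative, and the textual finding does not depend on it.

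Inputs: 15 AL, 15 TTR and 15 controls, of whom 10 have HFpEF and 5 do not (Synopsis; Protocol I.b). Assumptions: amyloid SD = 1, control SD = r, approximate normality.

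Half-width = t(0.975, df) × √(1/n₁ + r²/n₂), with df = (1/n₁ + r²/n₂)² / [(1/n₁)²/(n₁−1) + (r²/n₂)²/(n₂−1)].

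With r = 1:
- Amyloid vs control, 30 vs 15: √(1/30 + 1/15) = 0.316; df = 28.1; t = 2.048; half-width 0.648 SD. The pooled-variance version (df 43, t = 2.017) gives 0.638.
- AL or TTR vs control, 15 vs 15: √(2/15) = 0.365; df = 28; t = 2.048; half-width 0.748 SD.
- One subtype vs the 10 HFpEF controls: √(1/15 + 1/10) = 0.408; df = 19.4; t = 2.090; half-width 0.853 SD.
- One subtype vs the 5 other volunteers: √(1/15 + 1/5) = 0.516; df = 6.9; t = 2.372; half-width 1.225 SD.

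For r from 0.5 to 1.5, the 30 vs 15 half-width runs from 0.451 to 0.892, and the 15 vs 15 half-width from 0.601 to 0.960. For a subtype contrast, the choice of control set alone moves the half-width from 0.75 to 1.23 SD when SDs are equal.

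**4. Why the pooled contrast needs the subtype contrasts beside it.** With equal subtype sizes, the pooled difference is (d_AL + d_TTR)/2. If the tracer bound one type only, with difference d, the pooled difference would be d/2.

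**5. Sample sizes.** The 30 and 15 are not uniform across the Protocol. Section II gives 10 individuals with and 5 without cardiac amyloidosis, and section IV.a refers to 25 subjects. At 10 vs 5 with equal SDs: √(1/10 + 1/5) = 0.548; df = 8.1; t = 2.301; half-width 1.26 SD.

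**The case against.** The strongest reply is that the comparison is implied. Controls are scanned, the Synopsis measures uptake without a group limit, and the visual score, the liver-to-heart ratio and the wording of Protocol VI are all open to controls. Much of this stands. A reader might infer that control uptake will not be measured, or that the whole plan is blind to non-binding. The documents support neither reading. What remains is that none of these elements is given a stated contrast, and that the one sentence on uptake in the SAP excludes controls.

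A second reply is that this is a pilot feasibility study and needs no power calculation. That is right, and a reader should not take the half-widths to mean that the study is too small, since no target is given to judge it against. The point asks only for estimates that match the aim.

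A third concerns timing. The SAP describes SUV measurement in the past tense, from which a reader might infer that any added contrast is wholly post hoc. But the SAP is dated January 2018, the Protocol gives enrolment to October 2018, and the SAP's statistical text is in the future tense. The most that can be said is that some SUVs may already have been measured.

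Finally, a control contrast is not a pure measure of binding. If background differs between groups by b, the contrast shifts by b, and the background section leaves this open for AL.

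**Conclusion.** The concern holds in this form: the SAP and Synopsis restrict the uptake estimates to amyloid subjects, Protocol VI is unclear, and no statistical section states a control uptake estimate or an amyloid-versus-control difference, although the primary aim includes 15 controls. Followed as written, the uptake analysis has no reference for separating amyloid uptake from background.

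The gap can be closed from planned scans, which is why it should be fixed but does not undermine the study. The finding rests on the text. The precision figures (about 0.65 SD for 30 vs 15 and 0.75 SD for 15 vs 15) rest on assumed equal SDs and on the 30 and 15 being the intended sizes.

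**What to change.** Reconcile the statistical text of the Synopsis, Protocol VI and the SAP as follows.

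1. Estimate left ventricular SUVmean and the liver-to-heart ratio with 95% CIs in amyloid subjects (overall, and by AL and TTR) and in all 15 controls. Also show the 10 HFpEF subjects and the 5 other volunteers separately.
2. State the amyloid minus control difference in SUVmean (30 vs 15), with a 95% CI that allows unequal variances, as the analysis of the primary aim. This matches the two groups named in the SAP.
3. Report AL minus control and TTR minus control with 95% CIs as supporting estimates, each read separately. Keep AL vs TTR descriptive.
4. Define maximal uptake in the SAP Imaging Methods, or drop it from the Statistical Methods.
5. Say that a difference reflects specific uptake only if background is similar across groups.
6. Reconcile the sample sizes in Protocol sections II and IV.a with the 30 and 15 given elsewhere.
7. Date the change, and record which SUVs had been measured by then.

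**Cost:** edits to wording and a little more analysis, with no new subjects, scans or readers. The downsides are wide intervals, and contrasts that may not count as fully prespecified.
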